4. DEFINITION OF TERMS

Data will be censored at 60 days for all outcomes from the date of last patient recruited.

Term	Definition
Unassisted breathing	No ventilatory support is defined as; extubated with supplemental oxygen or room air, or open T-tube breathing, or tracheostomy mask breathing, or CPAP without inspiratory pressure support for 48 hours. Patients receiving pressure support via non-invasive ventilation (except for sleep disordered breathing) or extra-corporeal lung support will be defined as receiving ventilatory support.
Discharge from critical care	First discharge to a ward in the hospital or another hospital; a transfer between ICUs is not considered a discharge from critical care. Hospital discharge is the first date that the patient is discharged to home/community, a transfer between hospitals is not considered as a hospital discharge.
Ventilator free days (VFDs) to day 28	
The number of days from the time of initiating unassisted breathing to day 28 after the date of commencing ventilatory support, assuming survival for at least 48 hours after initiating unassisted breathing and continued unassisted breathing to day 28. If the patient was receiving ventilatory support prior to ICU admission, the ICU admission date will be considered as the start of the VFD calculation. If a patient returns to assisted breathing and subsequently achieves unassisted breathing to day 28, VFDs will be counted from the end of the last period of assisted breathing to day 28. A period of assisted breathing lasting less than 24 hours and for the purpose of a surgical procedure will not count against the VFD calculation. If a patient was receiving assisted breathing at day 27 or dies prior to day 28, VFDs will be zero. Patients transferred to another hospital or other health care facility will be followed to day 28 to assess this endpoint.
 
The number of days alive and free from ventilation between final successful weaning and day 28 after study enrolment.
 $VFD = \begin{cases} (28 - x), & \text{if patient alive at day 28 and } x \leq 27 \\ 0, & \text{if patient requires mechanical ventilation for 28 days or more} \\ 0, & \text{if patient died within 28 days or } x > 27 \end{cases}$ 
Where x is number of days until patient achieved unassisted breathing

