5. SAMPLE SIZE CALCULATIONS

Data from several retrospective analyses have shown that the percentage of patients with ARDS in the hyper-inflammatory sub-group was 27-34% of the overall population, that the mortality in the hypo-inflammatory sub-group was 17-23%, with a mortality difference between the hyper-inflammatory and hypo-inflammatory sub-groups ranging from 15-32%. A conservative percentage of patients in the hyper-inflammatory sub-group of 25%, a mortality in the hypo-inflammatory sub-group of 17% and a difference in 28-day mortality between the hyper-inflammatory and hypo-inflammatory sub-groups of 15% was assumed. The mortality in the hyper-inflammatory group is assumed to be 17% under the null hypothesis and 32% under the alternative hypothesis [7-10].

Based on a two group chi-square test, group sizes of 347 in the hypo-inflammatory group and 116 in the hyper-inflammatory group achieves 90% power at a two-sided significance level of 0.05 to detect a mortality difference between the groups of 15%. Based on our previous experience the group sizes

have been inflated by 10% to allow for technical failure, drop-out or loss to follow-up giving group sizes of 386 in the hypo-inflammatory group and 129 in the hyper-inflammatory group. As such, at least 515 patients with ARDS will be recruited.

An additional exploratory cohort of patients with COVID-19 will be recruited. No formal sample size calculation for this cohort is feasible. An indicative sample of up to 100 patients will be recruited in this cohort during the course of the study, however it is recognized that this is an estimate which will be dependent on the duration of the COVID-19 pandemic.

A further exploratory cohort of up to 300 patients with AHRF will be recruited. No formal sample size calculation for this cohort is feasible as these subphenotypes have not been described in such AHRF patients before. A sample of 300 patients is required in order to provide a minimum sample to undertake latent class analysis.

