7.4 Additional analysis

To study the performance of the New Global Definition of ARDS [12], primary and secondary outcomes will be reported for the entire study cohort, the study cohort stratified by ARDS severity as defined by the New Global Definition of ARDS [12], and the study cohort stratified by ARDS severity as defined by the Berlin Definition of ARDS [6].

An additional analysis will be conducted on the cohort of patients with AHRF, to assess the proportion of patients developing ARDS by phenotype. This will be reported as absolute number and percentage, with p value for difference between phenotypes from Fisher's exact test. In AHRF developing ARDS, the median (IQR) number of days to ARDS development will be calculated by phenotype, with p value for difference between phenotypes from Mann Whitney U test.

Outcomes will be compared within a given phenotype with respect to ARDS/AHRF diagnosis. Primary and secondary outcomes will be compared for all hyperinflammatory patients (ARDS vs. AHRF) and all hypoinflammatory patients (ARDS vs. AHRF). Comparisons will be made using Fisher's exact test for categorical outcomes and Mann-Whitney U Test for continuous outcomes.

Subsequent analyses after study completion may explore the relationship between hyperinflammatory and hypoinflammatory phenotypes and other ARDS phenotypes [13] and sepsis phenotypes [14,15] as well as the use of varying probability cutpoints for phenotype assignment in comparison to full latent class analysis.

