- patients receiving mechanical ventilation
- patients receiving non-invasive ventilation
- patients receiving high flow nasal oxygen
- patients receiving high-flow nasal oxygen with a flow rate of at least 30 litres per minute
- analysis excluding COVID-19 patients
- analysis restricted to patients with biosamples obtained within 24h of ARDS diagnosis
- analysis restricted to patients with biosamples obtained within 48h of ARDS diagnosis

Additional analysis

- Primary and secondary outcomes for the total cohort
- Primary and secondary outcomes for the total cohort, stratified by severity as defined by the New Global Definition of ARDS [12]
- Primary and secondary outcomes for the total cohort, stratified by severity as defined by the Berlin Definition of ARDS [6]
- ARDS development among patients with AHRF, absolute number and percentage. Comparisons made stratified on phenotype allocation.
- Time to ARDS development in patients with AHRF developing ARDS, median (IQR) number of days. Comparisons made stratified on phenotype allocation.
- Primary and secondary outcomes within each phenotype with respect to ARDS/AHRF diagnosis
- Comparison of hyperinflammatory and hypoinflammatory phenotypes to other ARDS phenotypes [13]
- Comparison of hyperinflammatory and hypoinflammatory phenotypes to sepsis phenotypes [14,15]
- The use of varying probability cutpoints for phenotype assignment in comparison to full latent class analysis

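### Days to ARDS are compared only among AHRF patients who develop ARDS, so the Mann-Whitney p-value cannot be read as a difference in the rate or timing of progression

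*Supplement*

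**What the plan says.** Section 7.4 plans two comparisons of ARDS development by phenotype in the AHRF cohort.

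- **Proportion developing ARDS, all AHRF patients:** "This will be reported as absolute number and percentage, with p value for difference between phenotypes from Fisher's exact test".
- **Days to ARDS, developers only:** "In AHRF developing ARDS, the median (IQR) number of days to ARDS development will be calculated by phenotype". The phenotypes are then compared by a Mann-Whitney test.

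The list in Section 8.5 keeps the same population for the second analysis: "Time to ARDS development in patients with AHRF developing ARDS, median (IQR) number of days".

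Section 4 has a general censoring rule ("Data will be censored at 60 days for all outcomes from the date of last patient recruited") but no entry for time to ARDS. Neither Section 7.4 nor Section 8.5 says how death, discharge or recovery before ARDS enters the comparison.

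On size, Section 5 says "A further exploratory cohort of up to 300 patients with AHRF will be recruited" and adds "No formal sample size calculation for this cohort is feasible as these subphenotypes have not been described in such AHRF patients before".

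**The concern.** Developing ARDS happens after baseline, and the time comparison selects on it. Patients who die, go home or recover without ARDS contribute no time at risk. The times that remain are those of patients whose ARDS came before any other exit. Their distribution therefore depends on the ARDS rate and on the rate of all other exits together.

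If the phenotypes differ in how quickly they leave the risk set, two misreadings become possible. Equal ARDS rates can give a significant difference in days, and the phenotype that stays ill longer then appears to progress later. Conversely, a real difference in ARDS rate can leave the developers' times unchanged.

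Unequal exit is plausible here. The study hypothesis (Section 1) is that hyper-inflammatory patients do worse, and the secondary outcomes compare mortality, ventilation and length of stay by phenotype. At stake is how a reader interprets the plan's only time-based statement about phenotype and progression from AHRF to ARDS.

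**Working it through.** **The plan's own figure.** No power or event rate is given for the AHRF cohort. The only power figure is for ARDS mortality: 347 v 116 patients, 17% v 32%, 90% power. A two-proportion calculation gives 91%. The inflation also reproduces: 347/0.9 = 386, 116/0.9 = 129, total 515. None of this bears on the AHRF time test.

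**Inputs.**
- Cohort: up to 300 (Section 5).
- Hyper-inflammatory share: 25%, planned for ARDS and borrowed here as an assumption. 300 × 0.25 = 75, leaving 225.
- Two-sided 5% level: stated for the ARDS comparison, assumed here.
- ARDS hazard λ and other-exit hazard μ, constant per day: assumptions throughout.
- Horizon: 60 days matches the censoring rule in Section 4; 28 and 7 days are alternatives.

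**Closed form, ignoring the horizon.** The density of ARDS times is λe^(−(λ+μ)t), and the proportion who develop ARDS is λ/(λ+μ). Dividing gives the developers' density, (λ+μ)e^(−(λ+μ)t), with median ln 2/(λ+μ). Only the sum λ+μ matters.

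- ARDS hazard doubled, 0.08 v 0.04, exits 0.08 v 0.12: both sums are 0.16, so both medians are 0.693/0.16 = 4.3 days, although 50% v 25% develop ARDS.
- ARDS hazards equal at 0.04, exits 0.08 v 0.12: medians 0.693/0.12 = 5.8 v 0.693/0.16 = 4.3 days, with no difference in ARDS hazard.
- ARDS hazard doubled, 0.06 v 0.03, exits 0.10 in both: medians 4.3 v 5.3 days, only one day apart, with 37.5% v 23% developing ARDS.

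**Simulated rejection with equal ARDS hazards** (hyper v hypo; paired figures are separate runs):

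| Horizon | ARDS hazard, both | Other exits | Mann-Whitney | Fisher | Cause-specific log-rank |
|---|---|---|---|---|---|
| 28 d | 0.04 | 0.08 v 0.12 | 13–15% | 23% | 4–5% |
| 28 d | 0.04 | 0.08 v 0.16 | 34–35% | 55% | 4–5% |
| 28 d | 0.04 | 0.10 v 0.10 | 4.5% | not run | 5.1% |
| 7 d | 0.04 | 0.08 v 0.12 | 5.3% | not run | not run |
| 7 d | 0.04 | 0.08 v 0.16 | 8.6% | not run | not run |
| 60 d | 0.03 | 0.05 v 0.10 | 41% | 63% | 5.1% |
| 60 d | 0.03 | 0.10 v 0.10 | 4.9% | 4.5% | 5.3% |

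A further 7-day run gave about 6% for Mann-Whitney. A short horizon removes most of the distortion because the developers' times in both groups are then squeezed towards an even spread over the same few days.

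**Simulated power with the ARDS hazard doubled:**

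| Horizon | ARDS hazard | Other exits | Mann-Whitney | Fisher | Cause-specific log-rank |
|---|---|---|---|---|---|
| 28 d | 0.08 v 0.04 | 0.08 v 0.12 | 5% | 97–98% | 91–92% |
| 28 d | 0.08 v 0.04 | 0.10 v 0.10 | 15% | 68–73% | 87–88% |
| 60 d | 0.02 v 0.01 | 0.10 v 0.10 | 6% | 40% | 50% |
| 60 d | 0.10 v 0.05 | 0.05 v 0.05 | 53% | 71% | 98% |
| 60 d | 0.04 v 0.02 | almost none | 56% | 98% | over 99% |
| 60 d | 0.06 v 0.03 | 0.20 v 0.10 | 53% | 4% | 66% |

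The last row is built so that the proportions are equal: 0.06/0.26 = 0.03/0.13 = 23%. Fisher then sees nothing although the ARDS hazard is doubled. Together with its 23–63% rejection in the unequal-exit rows of the first table, this shows that the proportion test does not separate ARDS rate from time at risk either.

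**The case against.** A reader might infer that the plan would miss a doubled ARDS rate. The documents do not support that. The sentence before the time analysis tests the proportion developing ARDS in the whole AHRF cohort. Apart from the constructed equal-proportion case, Fisher's power for a doubled hazard was about 40–98%. With exits of 0.08 v 0.12 it does at least as well as the log-rank test. This stands, and it limits the point to the time test.

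It can also be said that the SAP states openly that it describes time among developers and claims no hazard. Proportion and timing are different questions, so different answers need not contradict each other. As a description, the conditional median is legitimate. The p-value for a phenotype difference is what invites the stronger reading, and that part of the concern remains.

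The distortion also depends on invented inputs. The documents give no AHRF exit rates. The ARDS mortality assumption in Section 5 (32% v 17%) implies faster exit by death in hyper-inflammatory patients, which could offset slower recovery, so even the direction is unknown. Section 1 requires ARDS onset within a week of the insult and excludes patients more than 72 hours after onset of AHRF. If progression is mostly early, the false-rejection problem largely disappears. All of this stands. It makes the size uncertain but does not make the p-value interpretable.

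Finally, the analysis is an additional one in an exploratory, unpowered cohort. That lowers the severity.

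**Conclusion.** The point holds in limited form and is minor. The structural part needs no assumed rates: a comparison restricted to developers is governed by total exit from the risk set. Its p-value cannot be taken as evidence that phenotype changes the rate or timing of progression to ARDS.

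The size is conditional. False rejection is about 13–35% over 28 days under the assumed exits of 0.08 v 0.12–0.16 per day. It is near nominal if progression is confined to the first week or if exits are equal, and larger over 60 days with a twofold difference in exit. Power of the time test for a doubled ARDS hazard is often low (5–16% in many settings) but reaches about 53–56% in some.

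These figures rest on constant hazards, assumed rates and a 25% hyper-inflammatory share carried over from ARDS. They do not show that the study's result will be wrong or reversed, only that the planned p-value could not tell the explanations apart. The primary outcome is unaffected.

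**What to change.** In Sections 7.4 and 8.5, define time from enrolment to ARDS in all AHRF patients. Report the cumulative incidence of ARDS by phenotype, with death and discharge without ARDS as competing events. Take the phenotype p-value from a cause-specific log-rank test or Cox model, with a hazard ratio and 95% CI. Keep Fisher's test of the proportion. Keep the developers' median (IQR) as description and drop its Mann-Whitney p-value.

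The cost is SAP wording and one added output. The completion schedule in Section 3.3 lists forms for development of ARDS, death and discharge. The duration formulas in Section 4 already use dates of death and discharge, and the planned days-to-ARDS summary needs the ARDS date. The team should confirm that these dates are held for the AHRF cohort. Recovery without ARDS has no definition in Section 4, so discharge is the simpler competing event unless one is added. The price in presentation is that a curve and a hazard ratio take more explaining than two medians.

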8. ANALYSIS DETAILS

[figure not shown]
The results of the analyses will be reported following the principles of the ICH E3 guidelines on the Structure and Content of Clinical Study Reports.

8.1 Recruitment and withdrawal patterns

The recruitment and withdrawal patterns will be reported as follows:

- Recruitment by year, centre.
- Withdrawals by site - this should include the timing of withdrawals.

8.2 CONSORT Flow Diagram

8.3 Baseline Characteristics

Descriptive analysis will be conducted for the following baseline characteristics, by phenotype and total. Where mean (SD) is specified, median and interquartile range will also be calculated and presented if more appropriate based on the distribution:

- Age (years), mean (SD) by phenotype and total
- Sex, n (%) by phenotype and total
- Ethnicity, n. (%) by phenotype and total
- Height (cm), mean (SD) by phenotype and total
- Weight (kg), mean (SD) by phenotype and total
- Predicted body weight (kg), mean (SD) by phenotype and total
- Body mass index (kg/m²), mean (SD) by phenotype and total
- Cigarette smoking status (current smoker, past smoker and never smoked), n (%) by phenotype and total
- Current smokers (Number of years smoked and Average smoked per day), mean (SD) by phenotype and total
- Past smokers (Number of years smoked and Average smoked per day), mean (SD) by phenotype and total
- Past smokers (Not known), n (%) by phenotype and total
- Number of years e-smoking, mean (SD) by phenotype and total
- Type of e-smoking device (disposable, refillable, voltage variable, other, not known), n (%) by phenotype and total
- Amount of e-liquid used per day (mls), n (%) by phenotype and total
- Does the e-liquid used by the patient contain nicotine (Yes/No), n (%) by phenotype and total
- Nicotine content of e-liquid (Per Week) (5mg/ml, 10mg/ml, 15 mg/ml, 20 mg/ml, other, not known), n (%) by phenotype and total
- Past e-smokers (Number of years e-smoking and Number of years since stopped e-smoking), mean (SD) by phenotype and total
- Past e-smokers (Not known), n (%) by phenotype and total
- Alcohol use (Yes/No), n (%) by phenotype and total
- Average units of alcohol consumed per week, mean (SD) by phenotype and total
- Co-morbidities (Yes results for Congestive Heart Failure, Myocardial infarction, COPD, Asthma, Diabetes, Chronic Liver Disease, Cancer, Chronic Renal Failure, Other), n (%) by phenotype and total
- Aetiology of ARDS (Yes results for Smoke/toxin inhalation, Gastric content aspiration, Near drowning, Thoracic trauma, Pneumonia, Sepsis, Cardiopulmonary bypass, Pancreatitis, Non-thoracic trauma, Other), n (%) by phenotype and total
- APACHE II score, mean (SD) by phenotype and total
- Vital signs (Temperature (°C), Heart rate (bpm), Systolic blood pressure (mmHg), Diastolic blood pressure (mmHg)), mean (SD) by phenotype and total

- Haematology (Haematocrit (L/L), White Cell Count (x10⁹/L), PT (s), Fibrinogen (g/L)), mean (SD) by phenotype and total
- Biochemistry (Sodium (mmol/L), Glucose (mmol/L), Albumin (g/L), AST (U/L), ALT (U/L)), mean (SD) by phenotype and total
- First qualifying P/F ratio, mean (SD) by phenotype and total
- Worst P/F Ratio, mean (SD) by phenotype and total
- P/F Ratio closest to but prior to patient recruitment, mean (SD) by phenotype and total
- pH, mean (SD) by phenotype and total
- Lactate, mean (SD) by phenotype and total
- Bicarbonate, mean (SD) by phenotype and total
- PaCO₂, mean (SD) by phenotype and total
- PaO₂, mean (SD) by phenotype and total
- FiO₂, mean (SD) by phenotype and total
- Mode of Ventilation (Yes results for SIMV, APRV, HFOV, BIPAP, PC, PRVC, PS, NIV, HFNO, CPAP/ASB, Other, None), n (%) by phenotype and total
- Minute Volume (ml), mean (SD) by phenotype and total
- Total Respiratory Rate, mean (SD) by phenotype and total
- Mean Airway Pressure (cmH₂O), mean (SD) by phenotype and total
- Plateau Pressure (cmH₂O), mean (SD) by phenotype and total
- PEEP (cmH₂O), mean (SD) by phenotype and total
- Tidal Volume (Minute Volume/Total Respiratory Rate), mean (SD) by phenotype and total
- Tidal Volume (ml/kg PBW), mean (SD) by phenotype and total
- Respiratory Compliance (ml/cmH₂O), mean (SD) by phenotype and total
- Oxygenation Index (OI), mean (SD) by phenotype and total
- Total SOFA score, mean (SD) by phenotype and total
- Use of Adjunctive Therapies (Yes results for Airway Pressure Release Ventilation (APRV), High-Frequency Oscillatory Ventilation (HFOV), Neuromuscular Blocking Drugs (NMBD), Nitric Oxide, Prone Position, ECCO₂R, Other) n (%) by phenotype and total
- Murray Lung Injury Score, mean (SD) by phenotype and total
- Steroid Treatment on day 0 (Yes/No), n (%) by phenotype and total
- Type of steroid used (Hydrocortisone, Prednisolone, Dexamethasone, Methylprednisolone, Fludrocortisone, Other), n (%) by phenotype and total
- Total daily steroid dose, mean (SD) by phenotype and total
- Statin Treatment on day 0 or within last 7 days (Yes/No), n (%) by phenotype and total
- Type of statin used (Pravastatin, Atorvastatin, Simvastatin, Rosuvastatin, Other), n (%) by phenotype and total
- Total daily statin dose, mean (SD) by phenotype and total
- Insulin Treatment on day 0 (Yes/No), n (%) by phenotype and total
- Total daily insulin dose, mean (SD) by phenotype and total
- Enteral feeding on day 0 (Yes/No), n (%) by phenotype and total
- Total daily calories given, mean (SD) by phenotype and total

- Child Pugh Score, mean (SD) by phenotype and total
- Renal replacement therapy (Yes/No), n (%) by phenotype and total
- Does the patient have COVID-19? (Yes/No), n (%) by phenotype and total
- How was COVID-19 diagnosed? (Yes results for Clinical diagnosis, PCR diagnosis), n (%) by phenotype and total

8.4 Study withdrawal and protocol deviations

The withdrawal pattern will be analysed and reported using patients as unit of measure, as follows:

- Withdrawal of consent, n (%) by phenotype and total
- Type of consent withdrawn (Yes results for Use of data already collected, Ongoing data collection during hospital admission, Long term storage of research samples, Confirmation of vital status), n (%) by phenotype and total

The pattern of protocol deviations will be analysed and reported using both events and patients as unit of measure, as follows:

- Protocol deviations related to eligibility, n (%) by phenotype and total
- Protocol deviations related to consent, n (%) by phenotype and total
- Protocol deviations related to sample not taken, n (%) by phenotype and total
- Protocol deviations related to POC assay result not available, n (%) by phenotype and total
- Other protocol deviations, n (%) by phenotype and total

8.5 Study Outcomes

Primary outcome:

- Mortality at 60 days in patients with ARDS as defined by the POC assay, reported as n (%) by phenotype, unadjusted percentage point difference (95% CI), risk ratio (95% CI), and p value from Pearson's chi-square test

Secondary outcomes:

- Mortality at 60 days in patients with ARDS as defined by the POC assay, reported as odds ratio (95% CI) and p value from adjusted logistic regression (adjusted for age and gender)
- Mortality at 60 days in patients with ARDS defined by commercially-available laboratory assays and parsimonious models, reported as n (%) by phenotype, unadjusted percentage point difference (95%, CI), risk ratio (95% CI), and p value from Pearson's chi-square test (95% CI).

- Mortality at 60 days in patients with ARDS defined by the complete data-set using latent class analysis, reported as n (%) by phenotype, unadjusted percentage point difference (95% CI), risk ratio (95% CI), and p value from Pearson's chi-square test (95% CI).

For further secondary analyses, the assumption of normal distribution will be checked graphically for each continuous variable, but we anticipate using the following tests (alternative in brackets).

- Time to extubation, mean (SD) by phenotype, difference in means (95% CI) and p value from two-sided t-test for unpaired data (Mann-Whitney test)
- Intubation rate in patients receiving HFNO, number (%) by phenotype, percentage point difference (95% CI), and p value from chi-square test
- Re-intubation rate, number (%) by phenotype, percentage point difference (95% CI), and p value from chi-square test
- Ventilator free days at day 28, mean (SD) by phenotype, difference in means (95% CI) and p value from t-test for unpaired data (Mann-Whitney test)
- Duration of ventilation, mean (SD) by phenotype, difference in means (95% CI) and p value from t-test for unpaired data (Mann-Whitney test)
- Length of ICU stay, median (IQR) by phenotype, p value from Mann-Whitney test
- Length of hospital stay, median (IQR) by phenotype, p value from Mann-Whitney test
- 28-day mortality, n (%) by phenotype, unadjusted percentage point difference (95% CI) and Risk ratio (95% CI) and p value from chi-square
- Time to extubation, difference in means (95% CI) adjusted for age, co-morbidity, aetiology of ARDS, vasopressor requirement and PF ratio. P-values will be from ANCOVA.
- Intubation rate in patients receiving HFNO, percentage point difference/ RR adjusted for age, co-morbidity, aetiology of ARDS, vasopressor requirement and PF ratio. P-values will be from log binomial regression.
- Re-intubation rate, percentage point difference/ RR adjusted for age, co-morbidity, aetiology of ARDS, vasopressor requirement and PF ratio. P-values will be from log binomial regression.
- Ventilator free days at day 28, difference in means (95% CI) adjusted for age, co-morbidity, aetiology of ARDS, vasopressor requirement and PF ratio. P-values will be from ancova

- Duration of ventilation, difference in means (95% CI) adjusted for age, co-morbidity, aetiology of ARDS, vasopressor requirement and PF ratio. P-values will be from ancova.
- 28-day mortality, percentage point difference/RR adjusted for age, co-morbidity, aetiology of ARDS, vasopressor requirement and PF ratio. P-values will be from log binomial regression.

Agreement of phenotype classification:

- Agreement of phenotype classification using POC-derived phenotype versus phenotype from commercially available assays (defined by up to 8 different parsimonious logistic regression models [5]), Cohen's kappa coefficient and p value from McNemars test
- Agreement of phenotype classification using POC-derived phenotype and LCA-derived phenotype, Cohen's kappa coefficient and p value from McNemars test
- Agreement of phenotype classification using POC-derived phenotype and phenotype from clinical classifier machine learning algorithm [11], Cohen's kappa coefficient and p value from McNemars test
- Agreement of phenotype classification between baseline and day 3, by (i) latent transition analysis (LTA) and (ii) POC-derived phenotype at day 0 and day 3, reporting Cohen's kappa coefficient and p value from McNemars test
- Probability of phenotype allocation generated by POC-derived classifier versus phenotype from commercially available assays and parsimonious logistic regression models [5]. Comparisons will be made using Bland-Altman plots

Feasibility outcomes:

Feasibility of delivering a POC assay in NHS/HSE intensive care setting as measured by assay technical failure rate, reported as absolute number and percentage of events. No inferential statistical analysis will be conducted.

Sensitivity analysis:

The primary outcome, secondary analyses of the primary outcome, and secondary outcomes (when pertinent) will be analysed as above for the following subgroups:

- AHRF cohort
- patients receiving mechanical ventilation
- patients receiving non-invasive ventilation
- patients receiving high flow nasal oxygen
- patients receiving high-flow nasal oxygen with a flow rate of at least 30 litres per minute
- analysis excluding COVID-19 patients
- analysis restricted to patients with biosamples obtained within 24h of ARDS diagnosis
- analysis restricted to patients with biosamples obtained within 48h of ARDS diagnosis

Additional analysis

- Primary and secondary outcomes for the total cohort
- Primary and secondary outcomes for the total cohort, stratified by severity as defined by the New Global Definition of ARDS [12]
- Primary and secondary outcomes for the total cohort, stratified by severity as defined by the Berlin Definition of ARDS [6]
- ARDS development among patients with AHRF, absolute number and percentage. Comparisons made stratified on phenotype allocation.
- Time to ARDS development in patients with AHRF developing ARDS, median (IQR) number of days. Comparisons made stratified on phenotype allocation.
- Primary and secondary outcomes within each phenotype with respect to ARDS/AHRF diagnosis
- Comparison of hyperinflammatory and hypoinflammatory phenotypes to other ARDS phenotypes [13]
- Comparison of hyperinflammatory and hypoinflammatory phenotypes to sepsis phenotypes [14,15]
- The use of varying probability cutpoints for phenotype assignment in comparison to full latent class analysis

